Study Participants/Sample Collection	Individuals presenting to KCCR or MNIMR with suspected COVID-19 infection will be assessed by clinical staff and clinical specimens (e.g. nose, throat or nasopharyngeal swab, sputum or bronchoalveolar lavage collected for diagnostic testing.									
	Sera fromnSARS-Cov-2 positive and negative patients will be used to validate a proof of concept Immunoassay.									
Statistical Analysis	Data will be analyzed using software Statistical Packages for Social Science (SPSS) version 22.0. Sensitivity, specificity, positive predictive value, negat predictive value, and diagnostic accuracy will be calculated using standar formulas. Kappa and McNemar tests will be performed to determine to concordance and discordance between test assays and real-time RT-qPC based methods.									

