2.0 Aim and study objectives

Aim

The aim of the project is to provide reliable diagnostic systems for the confirmation of the clinical diagnosis of COVID-19 in Africa from first infection through to recovery and immunity, with:

- RNA viral testing enabled for point of care (POC)
- Antibody titre testing for POC
- Sample to result time of less than one hour
- >90% sensitivity and specificity
- Compatibility for distributed production at low cost in Africa

Hypothesis

Test assays are as sensitive and specific as real-time RT-qPCR-based molecular methods.

Primary objective

To provide reliable diagnostic systems for the confirmation of the clinical diagnosis of COVID-19 in Africa from first infection through to recovery and immunity

Specific Objectives

The objectives are:

To use the front line testing facilities in NMIMR and KCCR, Ghana, as a testbed for a new POC nucleic acid diagnostic emerging from DTU (PATHPOD - detection of virus RNA), that is
 Protocol: AfriDx
 Page | 6
 Version: 1.0 20 December 2020

currently under clinical test in Europe and will be seeking Emergency Use Authorization (EUA) in the next 6 months.

Secondary Objective:

• To replace the BST and RT enzymes in the PATHPOD with BST and RT constructs designed by UCAM for low resource production in Africa and evaluate the AfriDX-RT-LAMP alongside the PATHPOD and standard RT-qPCR procedure

• To develop an Antibody Titre assay to proof of principle from a UCAM single-chain antibody (scFv) library and produce scFv constructs for low resource production of a lateral flow immunoassay (LFIA) in Africa (AfriMx).

• To evaluate combined batch testing as methodology adopted from normal veterinary protocols (but not widely used for human testing) and assess accuracy, cost and time benefits in epidemic testing pathways.

• To draft a plan to produce AfriDx in Africa for the African market, with outline analysis of socioeconomic and healthcare benefits.

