3.0 Study design

This study is a cross sectional experimental which involves the development and evaluation of two low cost point of care (POC) and rapid throughput NAT and SARS-Cov-2 antibody titre tests. This study has been organised into 9 works packages under the broad themes: Project management, development of point of care diagnostics, clinical study and field test, innovation and dissemination. The diagnostic performance of PATHPOD, a point of care viral detection system developed by DTU and adapted for SARS-Cov-2 viral assays will be evaluated with viral nucleic acid extracted from sputum, oral and nasal pharyngeal swabs. This evaluation will be conducted at KNUST, KCCR and NMIMR with assistance from DTU and TATAA using samples collected for both symptomatic patients and asymptomatic individuals, identified through contact tracing or through testing of healthcare workers. A comparative data with the currently used laboratorybased RT-qPCR will be obtained for the innovative RT-LAMP (PATHPOD) to produce information on sensitivity and specificity. After this initial evaluation of the PATHPOD, the low-cost systems (Boon-BST and Boon-RT production) developed at UCAM for expression and purification of the DNA polymerase Bst and a reverse transcriptase (RT), the enzymes used for the RT-LAMP assay in the PATHPOD system will be employed for local production these reagents. If successful, this locally produced reagents in Africa (AfriDx-RT-LAMP) will be tested on a subset of samples collected compare results to the existing PATHPOD system.

The high-affinity single-chain variable fragment (scFv) developed by UCAM (Proof of Concept Serological Test Development) for COVID-19 immunoassays will also be adapted in this study. The resulting proof of concept AfriMx system will be tested on a small number of serological samples that will be collected from individuals who test positive and negative for SARS-CoV-2. Boon-scFV production protocols and design principles for scFV immunoassays will be transferred and disseminated through training activities in Ghana (Training and Capacity Building).

Sample size and statistical analyses

NMIMR, KCCR are supporting the frontline of SARS-Cov-2 testing in Ghana using RT-qPCR. Their capacity is ~1500 tests/day. We envisaged a total of about 4000 tests from KNUST and KCCR.

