Data will be analyzed using software Statistical Packages for Social Sciences (SPSS) version 22.0. Sensitivity, specificity, positive predictive value, negative predictive value, and diagnostic accuracy will be calculated using standard formulas. Kappa and McNemar tests will be performed to determine the concordance and discordance between test assays and real-time RT-qPCR-based methods.

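### The only inference on concordance with RT-qPCR is a kappa test and a McNemar test, and neither measures an assay against the protocol's 90% accuracy aim

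*Protocol*

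**What the plan says.** Under the sample size and statistical analyses heading of Protocol section 3.0, the comparison with RT-qPCR has two parts.

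- Accuracy measures: "Sensitivity, specificity, positive predictive value, negative predictive value, and diagnostic accuracy will be calculated using standard formulas".
- Inference: "Kappa and McNemar tests will be performed to determine the concordance and discordance between test assays and real-time RT-qPCR-based methods". The Statistical Analysis row of the Protocol Summary repeats this.

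The protocol gives no null value or minimum acceptable size for kappa, and no rule for reading either test.

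The standard to be met is in section 2.0. The aim lists ">90% sensitivity and specificity", and the hypothesis is "Test assays are as sensitive and specific as real-time RT-qPCR-based molecular methods". On volume, section 3.0 says "We envisaged a total of about 4000 tests from KNUST and KCCR". It does not say how many of these will be paired PATHPOD and RT-qPCR results. The share of RT-qPCR positives is not given either; the samples are described only as "samples collected for both symptomatic patients and asymptomatic individuals".

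**The concern.** The text gives a kappa test the task of determining concordance. As usually run, that test has the null kappa = 0, meaning agreement no better than between two unrelated classifications. Rejecting it shows that the assay carries some information about RT-qPCR status. It does not show that sensitivity or specificity is near 90%, or that the assay matches RT-qPCR.

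McNemar does not fill the gap. It compares the number of false negatives with the number of false positives, so it asks whether the two methods call the same share of samples positive. An assay with many errors of both kinds in similar numbers passes.

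At stake is a report that states significant concordance and no significant discordance, is read as support for the hypothesis, and concerns an assay that misses a large share of infections.

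**Working it through.** **The plan's own figure.** The 4000 is an envisaged volume with no derivation behind it, so there is nothing to reproduce.

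**Inputs.** From the protocol: about 4000 tests, and the aim of more than 90% sensitivity and specificity. Assumed: all 4000 are paired with RT-qPCR; RT-qPCR positivity p from 2% to 50%; the kappa null is zero.

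**Formulas.** Let q be the share called positive by the assay.

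- Observed agreement: po = p × Se + (1 − p) × Sp
- Chance agreement: pe = pq + (1 − p)(1 − q)
- kappa = (po − pe)/(1 − pe)
- Null standard error: SE0 = √[pe + pe² − pq(p + q) − (1 − p)(1 − q)(2 − p − q)] / [(1 − pe)√n]
- z = kappa/SE0
- McNemar chi-square = (FN − FP)²/(FN + FP), without continuity correction

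**Step 1: an assay with Se = Sp = 70%, n = 4000.**

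| RT-qPCR positive | kappa | z |
|---|---|---|
| 2% | 0.05 | 7.7 |
| 5% | 0.11 | 11.8 |
| 10% | 0.19 | 16.0 |
| 30% | 0.36 | 23.5 |
| 50% | 0.40 | 25.3 |

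An assay 20 percentage points below the aim on both measures is highly significant throughout. With 2000 pairs the smallest z in this range is 5.4, and with 500 pairs it is 2.7 (both at 2% positivity). The result does not depend on all 4000 tests being paired.

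**Step 2: both named tests at 10% positivity, n = 4000 (400 positive, 3600 negative).**

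*Se 50%, Sp 95%.* FN = 200, FP = 180, TP = 200, TN = 3420. po = 3620/4000 = 0.905; q = 380/4000 = 0.095; pe = 0.0095 + 0.8145 = 0.824. kappa = 0.081/0.176 = 0.46; SE0 = 0.0158; z = 29.1. McNemar = 20²/380 = 1.05, not significant. Overall accuracy is 90.5%, although half of the positives are missed.

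*Se 30%, Sp 95%.* FN = 280, FP = 180. po = 0.885, pe = 0.840, kappa = 0.045/0.160 = 0.28, z = 18.0. McNemar = 100²/460 = 21.7, significant. Here McNemar does raise a flag.

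*Se 90%, Sp 90%, on the boundary of the aim.* FN = 40, FP = 360. po = 0.900, pe = 0.756, kappa = 0.144/0.244 = 0.59. McNemar = 320²/400 = 256, strongly significant.

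McNemar therefore passes the 50%/95% assay and flags the 90%/90% one. It does not rank assays by their distance from the aim.

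**Step 3: what intervals on the planned measures would show.** For the 50%/95% assay with 400 positives, the 95% interval for sensitivity is 0.50 ± 1.96 × √(0.5 × 0.5/400) = 0.451 to 0.549, far below 0.90. For a true sensitivity of 60%, the distance from 90% in standard errors taken at 90% is (0.60 − 0.90)/√(0.9 × 0.1/400) = −20.0 with 400 positives. With 80 positives (2% positivity) it is −8.9. The comparison with 90% separates poor assays clearly even at low positivity.

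**The case against.** The strongest reply is that the fault is partly read into the text. No null is stated, and kappa is itself a measure of agreement, so the sentence may be loose wording for reporting the coefficient. No kappa P value is named as the criterion of success, and an analysis plan not shown here may add intervals and benchmarks. All of this stands, and it is why the zero null is treated above as an assumption. What remains is that the protocol makes tests the means of determining concordance, and neither test, as ordinarily run, addresses the aim or the hypothesis.

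Secondly, sensitivity, specificity and the kappa value would be reported, and they would expose a poor assay: sensitivity of 50% or 30%, and kappa of 0.46 or 0.28 against 0.59 for a 90%/90% assay at the same positivity. This also stands. A reader might infer that a favourable conclusion is guaranteed whatever the device does; the documents do not support that, because no passage lets a kappa P value override the estimates.

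Thirdly, a reader might infer that any assay detecting virus at all would be declared concordant. That is not so either. At 55% sensitivity and specificity with 2% positivity and 4000 pairs, z = 1.8 (p = 0.075). For the antibody assay, which "will be tested on a small number of serological samples", the number is not given. With 20 positive and 20 negative sera (an assumption), a 70%/70% assay would fail to reach significance in about 26% of studies. The figures here should be taken to apply to PATHPOD only.

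Lastly, McNemar does catch some poor assays, such as the 30%/95% one. It is a partial safeguard, as the 50%/95% case shows.

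**Conclusion.** The point holds in limited form. The protocol's only stated inference on concordance is a pair of tests that do not measure distance from the 90% aim. If kappa is tested against zero, a 70%/70% assay is highly significant with about 4000 pairs at every positivity from 2% to 50%. At 10% positivity, a 50%/95% assay passes both tests on expected counts.

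This rests on three assumptions: the zero null, the positivity range, and thousands of paired results. The last matters least, since the 70%/70% result survives at 500 pairs. The consequence is a risk of a misleading sentence about significant concordance next to point estimates that say otherwise. It is worth correcting, but it does not invalidate the study.

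**What to change.** In section 3.0 and in the Statistical Analysis row of the Protocol Summary, replace the sentence on kappa and McNemar with wording to this effect:

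- Sensitivity and specificity against RT-qPCR will be reported with 95% confidence intervals, and the aim of more than 90% will be judged on those intervals.
- Cohen's kappa will be reported as an estimate with a 95% confidence interval.
- A test of kappa = 0 will not be used as evidence of concordance.

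Separate positive and negative agreement figures are not needed: against RT-qPCR they equal the sensitivity and specificity already planned. McNemar may stay as a description of the direction of disagreement.

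The change is a few lines in two places and needs no new data. It gives up a P value that would usually look favourable, and it makes a claim of more than 90% somewhat harder. If the claim requires the lower limit to exceed 90%, then with 400 positives an observed sensitivity of about 93% is needed (372/400, Wilson interval 90.1% to 95.1%).

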4.0 Research participants

Individuals suspected COVID-19 infection and presenting to KCCR, or KNUST and NMIMR with will be assessed by clinical staff and clinical specimens (e.g. nose, throat or nasopharyngeal swab, sputum or broncho-alveolar lavage collected for diagnostic testing upon giving their consent.

5.0 Study procedures

The overall study will be performed, after obtaining regulatory and IRB approvals as applicable in the country and the participating institutions. According to the study design, the diagnostic performance of PATHPOD, a point of care viral detection system developed by DTU and adapted for SARS-Cov-2 viral assays will be evaluated with viral nucleic acid extracted from sputum, oral and nasal pharyngeal swabs. This evaluation will be conducted at KNUST, KCCR and NMIMR with assistance from DTU and TATAA using samples collected for both symptomatic patients and asymptomatic individuals, identified through contact tracing or through testing of healthcare

Protocol: AfriDx Version: 1.0 20 December 2020 workers. A comparative data with the currently used laboratory-based RT-qPCR will be obtained for the innovative RT-LAMP (PATHPOD) to produce information on sensitivity and specificity. After this initial evaluation of the PATHPOD, the low-cost systems (Boon-BST and Boon-RT production) developed at UCAM for expression and purification of the DNA polymerase Bst and a reverse transcriptase (RT), the enzymes used for the RT-LAMP assay in the PATHPOD system will be employed for local production of these reagents and testing. If successful, this locally produced reagents in Africa (AfriDx-RT-LAMP) will be tested on a subset of samples collected compare results to the existing PATHPOD system.

The high-affinity single-chain variable fragment (scFv) developed by UCAM (Proof of Concept Serological Test Development) for COVID-19 immunoassays will also be adapted in this study. The resulting proof of concept AfriMx system will be tested on a small number of serological samples that will be collected from individuals who test positive and negative for SARS-CoV-2. Boon-scFV production protocols and design principles for scFV immunoassays will be transferred and disseminated through training activities in Ghana (Training and Capacity Building).

Nucleic acid extraction and RT-LAMP

Viral RNA will be extracted and purified from swab using the heating method.

Virus lysis

Samples will be collect from patient using the E-swabs according to standard protocol specified by WHO, CDC or ECDC. Each sample will be well labelled and stores at 4 oC for 5 min. The tube together with the sample will be vortex briefly to release the virus on the swab into the solution. The swab will be remove, and the solution heated at 95 0C for 5 min in a heat block or water bath to inactivate virus. The sample can be loaded on the chip or stored at - 20 °C until. **Isothermal amplification (RT-LAMP)**

The isothermal amplification will be conducted using the PATHPOD device.

Figure 2. The amplification cycle of LAMP showing forward, loop and backward primers.

The amplification depends on binding of the recombinase to oligonucleotide primers. The complex then scans the template DNA for the corresponding sequence and initiates 5'-strand invasion of the oligonucleotide at the site of homology. The strand invasion is stabilized by the single strand binding protein. The extension of the primer ensues via a strand displacing DNA polymerase

	Activities	Μ	M	Μ	Μ	Μ	Μ	Μ	Μ	Μ	Μ	Μ	Μ	Μ	М	Μ
		1	2	3	4	5	6	7	8	9	10	11	12	13	14	15
	Testing Strategy															
Table 1: Study	Development of study protocol and															
Time Frame	supporting documents															
	Development of comparative study															
	operational procedure and training															
	Institutional and Regulatory Approvals:															
	Sample collection and testing															
	Data Management and Analysis															
	Local Production of Boon-RT and BST in															
	Ghana for use in RT-LAMP assay															
	Reporting of study findings															
	Demonstration of COVID-19 antibody															
	detection via AfriMx immunoassay in Ghana															

6.0 Recruitment

Participants of this study include individuals suspected of contracting Covid-19 and are presenting to KCCR or KNUST and NMIMR. Their clinical specimens (e.g. nose, throat or nasopharyngeal swab, sputum or Broncho alveolar lavage collected for diagnostic testing upon obtaining an informed consent.

7.0 Consent process

The study will be explained to prospective participants who cannot read whereas those who can read and comprehend will be given the participant information leaflet from the CHRPE/IRB, that contains details of the study. Individuals who agree to take part in the study will have to give their consent by appending signature or thump printing the consent form.

8.0 Risks

Apart from minimal discomfort arising from sample collection, we do not anticipate any sever risk to the participants.

9.0 Mitigation of risks

The samples will be obtained by qualified clinicians/laboratory personnel. This will help in mitigating the risk.

10.0 Benefits

Even though there is no direct immediate benefit to the participant, successful completion of this study will be of use to the nation, continent and world at large. This will be achieved in the cost effective and rapid turnaround time of the device, not compromising on the sensitivity and specificity.

Again, all publications and relevant data will be made Open Access, training and capacity building activities aim to transfer knowledge and technology to the Ghanaian partners such that they are able to continue independent use and development of the technologies and engage in further international collaborations.

11.0 Study and safety monitoring

The investigator is responsible to ensure the accuracy, completeness, legibility, and timeliness of the process and data generated. All source documents should be completed in a neat, legible manner to ensure accurate interpretation of data. Site monitoring will be conducted to ensure that the human subject protection, study procedures, laboratory, study intervention administration, and data collection processes are of high quality and meet the regulatory guidelines.

Regular monitoring will be performed to ensure all the procedures are performed as per the approved protocol and the study is conducted as per ICH good clinical practice guidelines.

12.0 Managing and reporting adverse events

The study procedures do not involve intervention process to any study participants. We, therefore, do not envisage any adverse event. However, clinicians will be at the site of recruitment and sample taking to assist should any such event arise.

13.0 Managing and reporting unanticipated problems or protocol deviations

The investigator will report any deviation from an approved protocol or any study-related procedures to the PI by close of working day. Any serious deviations or unanticipated problems (e.g., a breach in confidentiality, changes at site that affect the conduct of the research, sample specification, etc.) will be managed and reported to the reviewing IRB/ethics committee and others as per their mentioned guidelines.

14.0 Confidentiality and data management

All sites will maintain the confidentiality of data collected from study participants as per the procedure defined in the consent forms according to regulations by the IRB/ethics committee. All samples will be labeled with random numbers by the site investigator.

Data obtained cannot be linked directly to any individual. All the data will be entered in a Microsoft Access database and kept safely with the PI. In reporting findings, by way of publication, unique codes will be used and not names.

15.0 Study costs

The study-related costs including pay for procedures associated with the study shall be covered by European and Developing Countries Clinical Trials Partnership (EDCTP). No costs will be incurred to any individual whose samples will be considered in the study.

16.0 Care for injury

We do not anticipate research-related injuries. Researchers handling participants and samples are encouraged to strictly comply by good laboratory practices. However, clinicians will be onsite to handle any of such unforeseen circumstances.

17.0 Compensation

We will compensate participants for the transportation costs and the time required to participate in this study. The minimum amount of GHS 20.00 will be given to the participants depending on the distance travelled. However, extra transportation cost incurred beyond GHS 50 will be reimbursed to participants.

